**Background, Rationale and Context**

The number of older adults is projected to increase dramatically by 2050. Aging-related diseases and conditions still seriously compromise the quality of life among most older adults. Several pharmaceutical agents (1-4), such as metformin, have been tested to extend lifespan and delay aging-related diseases and dysfunctions in mice. Metformin, a biguanide antidiabetic drug, reduces the risk for developing type-2 diabetes in persons at risk by over one-third with few adverse effects (e.g., gastrointestinal irritation) (5). Metformin prevents type-2 diabetes primarily through decreasing hepatic glucose synthesis (6), as well as enhancing insulin sensitivity and increasing peripheral glucose uptake (7-9). The molecular mechanisms remain unclear, although a number of potential mechanism such as activation of AMP-activated protein kinase (AMPK) and inhibition of mitochondrial glycerophosphate dehydrogenase have been proposed, see figure 1 (10;11). The fact that metformin treatment in persons with type-2 diabetes has been associated with reduced risk of other aging-related diseases and conditions, including cardiovascular

disease (12), cancer (13) and cognitive decline (14) supports the possibility of the beneficial effects of metformin on healthy aging. It is imperative to capitalize on these leads to extend health span among older adults.

Figure 1. Metformin targets multiple pathways of aging

To translate animal findings to human intervention trials, appropriate aging biomarkers are needed. Methylomic and transcriptomic profiles in relevant cells may reflect molecular features that mediate effects of both genetic and environmental factors on aging-related functional decline and disease. The roles of monocytes have been implicated in development of many aging-related diseases such as cardiovascular disease, cancer and neurodegenerative disease (15). In a cross-sectional

association study of 1,200 monocyte samples, we identified 1,794 age-associated methylation sites (16) and 2,704 age-associated transcripts (17), which were over-represented in two networks (autophagy and oxidative phosphorylation) and suggestive of decline in those functions with age. Both autophagy (18) and oxidative phosphorylation (19) are considered as key contributors to the aging process, and their dysfunctions have been linked to aging-related diseases (20;21). Changes in these aging-related omic biomarkers may be early indicators of cellular damage or disruption that eventually leads to age-related dysfunctions. Assessment of these aging biomarkers in response to therapeutic intervention may also

provide molecular insight for personalizing treatment. We propose a pilot study to examine changes in aging-related omic profiles after 3 months of metformin treatment in 35 monocyte samples from older adults using a randomized, double-blind, placebo-controlled crossover study design.

### **Objectives**

Our overarching goal of the pilot study is to evaluate the utility of using the aging-related omic biomarkers as an indicator of pharmacologic responses in the anti-aging therapeutic intervention trials through the following specific aims. Although this pilot study does not have sufficient power to definitively test all the aims, it will provide essential preliminary data for developing a full scale research program.

- Aim 1A: To test the effects of the metformin treatment on transcriptomic profiles and related functional changes in human monocytes,
- Aim 1B: To explore the effects of the metformin treatment on methylomic profiles in human monocytes,
- Aim 2: To investigate the longitudinal relationship between transcriptional and functional changes in human monocytes during the metformin treatment and
- Aim 3: To test the effects of the metformin treatment on frailty and other aging-related physical and cognitive measures and investigate the longitudinal relationship between these changes and transcriptional changes.

### **Methods and Measures**

#### **Design**

A randomized, double-blind, placebo-controlled crossover trial in 35 participants using metformin and matching placebo will be used. In the absence of a treatment by sequence interaction effect, this design can increase study power for evaluating treatment effects by allowing each participant to be his/her own control. The period effect may be minimum because the primary outcomes, methylation and transcriptional measures, are relatively stable overtime.

#### **Setting**

All visits will occur in the Geriatric Clinical Research Unit (G-CRU) or the Geriatric Research Center (GRC) in the Sticht Center on Aging.

#### **Subjects selection criteria**

All prospective participants in and around Forsyth County, NC will initially be screened via telephone to determine general eligibility. They will be asked about their age, medical history, and current medications. All participants must meet the inclusion/exclusion criteria below.

##### **Inclusion Criteria**

Age 65 – 79

Must meet criteria from one or more of the following groups:

##### **Group 1 (Can have 1 or 2 of these, but not all 3)**

- History of coronary artery disease (MI/heart attack, stroke, heart failure, or peripheral artery disease)
- Cancer, with no active treatment in the last year
- MCI (MoCA  $\geq 18 < 26$  –inclusive of 1 point if <12 years of education

##### **Group 2**

- Decline physical function (walking speed  $< 1$  m/s)

##### **Group 3 (Either or both)**

- Abdominal obesity ( $> 88$ cm women,  $> 102$ cm men) AND hypertension (treated or resting blood pressure  $> 140/90$

- Abdominal obesity (>88cm women, >102cm men) AND hyperlipidemia (treated or fasting total cholesterol >240

English literacy  
Willing to provide informed consent

**Exclusion Criteria**

eGFR <45  
Type 2 diabetes (HbA1c>6.5) or type 1 diabetes  
Any tobacco or nicotine product use in the past year  
Low vitamin B12 Levels (< 300 pg/mL)  
Self-reported severe difficulty or inability to walk 400m or climb 10 steps (from Q 2 and 19 on PAT-D)  
Self-reported difficulty or inability to perform basic ADL functions (from Q 10, 13, 14, 16 on PAT-D)  
Excessive alcohol use (>14 drinks/week)  
Cancer requiring treatment in past year (except skin)  
Dementia – diagnosed and/or MoCA score <18  
Parkinson's or other neurological disease  
Chronic liver disease or cirrhosis  
End stage renal disease or on dialysis  
Rheumatic conditions (Rheumatoid arthritis, lupus, and any other autoimmune disease the PI deems them to be ineligible for)  
Thyroid problems the PI deems them to be ineligible for  
Recent or recurrent exacerbation of gout  
Involved in another interventional study  
Hemoglobin  $\leq$ 8 or diagnosed with anemia  
Recent unintentional weight change (+/- 10 lbs. in the last 12 months)  
BMI <18.5  
Likely to not follow the protocol  
PI deems unfit to participate  
Already taking Metformin or any other drug intended to treat diabetes

***Screening, consent and randomization.*** Individuals who pass the telephone screening will be scheduled for a visit to the Geriatric Research Clinic (GRC) in the Sticht Center on Aging for a screening visit (SV). Before any data collection, all participants will provide written informed consent and complete a HIPAA authorization form in accordance with the Wake Forest School of Medicine Institutional Review Board policies. Individuals who meet all eligibility criteria and provide informed consent will be invited back for the first baseline visit (BV). At the end of BV, participants will be randomized to one of the two study intervention sequences (metformin followed by placebo or placebo followed by metformin) using a web-based randomization scheme (developed by [name]). The randomization sequences will be unknown to the research staff. Intervention assignment will be generated using a program that the study coordinator will access from his/her PC through the study website.

#### **Schedule and organization of assessment visits**

All assessments will be conducted during 4 visits (before and after each intervention) according to the chart below. All examiners are trained in the standardized conduct of all assessments before data collection. Participants will be instructed to wear appropriate and comfortable clothing, and standardized written instructions will be provided prior to each study visit.

Assessment timeline	Visit code	SV	BV	On trial	Mid	On trial	FV
Activity/assessment	Week number	-4	0		12-14		24-26
Informed consent, review inclusion/exclusion criteria, demographics, weight, height, BP and pulse, fasting screening blood draw (metabolic blood panel, lipid panel, CBC, Vit B12, Hba1c), eSPPB, cognitive screen (MoCA), waist circumference, medical history, medications PAT-D,		X					
Blood collection for methylomic and transcriptomic, bioenergetic capacity, CBC, and blood for storage, DSST, leg press, grip, MATsf, and 6MWD			X				
Randomization			X				
Crossover – Dispense New Medication					X		
Vitals, blood collection for methylomic and transcriptomic, bioenergetic capacity, and blood for storage, CBC, CMP, lipids, Hba1c, eSPPB, MoCA, DSST, leg press, grip, PAT-D, MAT-sf, 6MWD					X		X
Health Maintenance							X

The screening visit (SV) will be conducted in the morning following an 8-hour fast for measurement of lipids, blood count, Hba1c, Vitamin B12, and a metabolic panel for screening purposes. Vitals (blood pressure, pulse, height, weight, and waist circumference) are collected and the blood draw completed, participants will be given a snack and continue with the remainder of the visit. First, the expanded short physical performance battery (eSPPB) will be administered and scored and then undergo a cognitive screen, assessed using the Montreal Cognitive Assessment (MoCA), and a medical history, review of medications and dietary supplements. We will also ask about the participants demographics and physical abilities using the Pepper Assessment Tool for Disability (PAT-D),

The first baseline visit (BV), will be conducted in the morning following an 8-hour fast for blood collection for methylomic and transcriptomic measures, bioenergetic capacity, CBC, as well as blood for storage. After these measures are complete, participants will be given a snack and will continue with the rest of the visit consisting of lower extremity muscle power (Nottingham Power Rig), grip strength, 6 minute walk distance test (6MWD), and the Mobility Assessment Tool – short form (MAT-sf). Cognitive function will be assessed using the Digit Symbol Test (DSST). Once the visit is complete, the participant will be randomized and placed in one of the following groups discussed below. Participants will be provided with an information sheet that will provide additional details on how and when to take the medication, who to call if they have any problems, possible side effects, and what to do should they encounter any side effects.

#### Interventions and Interactions

Eligible participants will receive both interventions (3-month metformin treatment and 3-month placebo). Randomization will be used to determine the order in which the participants receive each intervention (i.e., 15 participants with metformin treatment followed by placebo, and 15 with placebo followed by metformin treatment). Neither the participants nor the investigators know the intervention order of a participant. Metformin reaches peak plasma concentration within one to eight hours, has an average elimination half-life of 6.2 hours in plasma, and is cleared but not metabolized from the body by tubular secretion. Treatment with metformin and placebo will be initiated at a dose of 425 mg taken orally once a day at night for 7 days. After the week, the participant will be called to assess tolerance and will be asked to increase dose to one pill at night at a dose of 850 mg for one week. At the end of the second week, participants will be called again and if they tolerated the second dose, they will be asked to take two 850mg pills, one in the morning and one at night, for a total dose of 1700 mg which is within the range of the usual effective dose of 1500 to 2000 mg/day for the remainder of the 3 months. This dosing regimen was created in order to avoid or reduce possible gastrointestinal side effects. This can be modified if the

participant is experiencing any side effects and will be handled on a case by case basis. Each study visit where stored blood is obtained (BV, Mid, FV) may be rescheduled if the subject has a fever, infection, or has taken antibiotics within 24hrs of this scheduled visit.

All baseline assessments will be completed again at 12 weeks and again at 24 weeks as listed in the assessment table.

### **Outcome Measure(s)**

The primary outcomes will be the eigengene scores (and related individual transcriptional measures) for the two transcriptional networks, the autophagy and oxidative phosphorylation. The eigengene score is defined as the first principal component of a transcriptional network. The secondary outcomes will include functional, methylation and other aging-related measures.

**Individual methylation sites and transcripts, especially the eigengenes of autophagy, oxidative phosphorylation and protein synthesis networks** Methylomic and transcriptomic profiles in monocytes will be quantified using the Illumina HumanMethylation450 BeadChip and the Illumina HumanHT-12 v4 Expression BeadChips, respectively, at [name] laboratory (22). Blood will be collected in Vacutainer CPTTM cell separation tubes containing sodium citrate (Becton Dickinson, Rutherford, NJ) to separate peripheral blood mononuclear cells. Then, monocytes will be isolated with the anti-CD14 coated magnetic beads using AutoMACs automated magnetic separation unit (Miltenyi Biotec, Bergisch Gladbach, Germany). DNA and RNA will be isolated simultaneously using the AllPrep DNA/RNA Mini Kit (Qiagen, Inc., Hilden, Germany).

**Functional measures:** An autophagic profile in monocytes including macroautophagy, microautophagy and chaperone-mediated autophagy will be measured using fluorescent reporters at [name] [name]'s lab in Albert Einstein College of Medicine.

**Mitochondrial Function: Respirometric profiling** will be used to assess bioenergetic capacity, respiratory control and electron transport chain function at [name] lab (23). This will be performed by examining the oxygen consumption profile of blood monocytes. Specific outcomes of mitochondria function include respiratory control ratio (RCR), state 3 (maximal oxygen consumption rate), and state 4 (oxygen consumption upon inhibition of ATP synthase).

### **Other Data**

**Vital Signs** Prior to randomization data are collected on sitting blood pressure, heart rate, and weight. Body height is measured once prior to randomization. The blood pressure assessments will allow the determination of the incidence of hypertension and serve as basis for a temporary exclusion. The other measures are collected primarily for descriptive purposes.

**Demographics and co-morbidities:** Medical information regarding co-morbidities and medications will be ascertained at the screening visit. Demographic data such as socio-economic status, education level, age, and race also will be recorded and used as covariates if necessary. Information about preventative health screenings and other health maintenance information is asked at the follow up visit.

**Physical performance** will be assessed using the expanded Short Physical Performance Battery (SPPB) (24). The expanded SPPB consists of 5 repeated chair stands, standing balance (semi- and full-tandem stands and a single leg stand for 30 seconds), a 4-m walk to assess usual gait speed, and a narrow 4-m walk test of balance (walking at usual pace within lines of tape spaced 20 cm apart). Scores for the traditional 0-12 point SPPB can also be obtained from these tests. We will also assess physical

performance using the six minute walk distance test (6MWD). The participant is asked to walk at a pace they can maintain for six minutes and the distance covered will be recorded.

**Lower extremity** muscle power will be measured using the Nottingham Power Rig, a safe, convenient method for assessing power output from the lower limb which has been used reliably in older adults. (25) Participants will sit in a chair and unilaterally depress a foot lever attached to a flywheel as hard and as fast as they can. Power output, derived from the acceleration of the flywheel, will be recorded in Watts. Power will be averaged for each leg following five trials at maximal effort. Participants that have had a unilateral hip or knee replacement should not have that side tested.

**Grip strength** will be measured twice in each hand to the nearest 2 kg using an isometric Hydraulic Hand Dynamometer (Jamar, Bolingbrook, IL) and the mean value from the stronger hand used. Participants will be excluded from performing the test if they report hand-pain or recent hand or wrist surgery.

**Cognitive function** will be assessed during screening using the Montreal Cognitive Assessment (MoCA) (26), participants must score  $\geq 18$  to be eligible. We will also assess psychomotor speed, attention, and working memory using the Digit Symbol Substitution Test (DSST) (27; 28). Participants are given a series of numbered symbols and then asked to draw the appropriate symbols below a list of random numbers. The score is the number of correctly made matches in 2 minutes (120 seconds).

**Body composition** will be measured by circumference measurements of the waist which is made with a tape measure.

**Blood lipids** (total cholesterol, HDL-Cholesterol, Triglycerides and calculated LDL levels) will be measured at a clinical lab and all results will be entered into the data system.

**Activities of daily living** will be assessed using the Mobility Assessment Tool – Short Form (MAT-sf). This is a novel, computerized tool for self-assessment of functional performance designed to reduce bias from factors such as age, gender and body image. The Pepper Assessment Tool for Disability (PAT-D) will also be used to assess the participant's ability to complete an array of important day-to-day activities without difficulty and, for a subset of activities, without personal assistance.

**Medication adherence:** Although we will attempt to enhance adherence by monthly calls to participants, there may be inter-individual variability in adherence to the medication. At the end of each phase, participants will be asked to return any unused pills for a pill count to determine participant adherence. Our primary analyses will be an intent-to-treat analysis of the effects of the metformin intervention, but secondary analyses will include adherence as a covariate.

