### **Analytical Plan**

We will use an analysis of variance model for crossover design to assess the effect of metformin on transcriptional profiles and other aging-related outcomes. The factors in the analysis will include the baseline measure, sequence, participant within sequence, period, and metformin treatment. We will explore for the metformin by sequence interaction and will base estimates of the metformin effect on whether this interaction effect is significant. We will also perform exploratory, linear regression analysis with transcriptional changes as the explanatory variables and changes in other aging-related measures as the outcome variables. The analysis will be focused on the eigengene scores of the autophagy and oxidative phosphorylation transcriptional networks (and related individual transcriptional measures). As this is a pilot study, focus of analyses will be on estimation of effects and constructing appropriate 95% confidence intervals for these effects.

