**TABLE 3. ADVERSE EVENTS.**

EVENT	PLACEBO	METFORMIN	LIFESTYLE
Gastrointestinal symptoms (no. of events/100 person-yr)*	30.7	77.8†	12.9†
Musculoskeletal symptoms (no. of events/100 person-yr)‡	21.1	20.0	24.1†
Hospitalization			
One or more admissions (% of participants)	16.1	15.9	15.6
Rate (no. of admissions/100 person-yr)	7.9	8.4	8.0
Median stay (days)	3	3	3
Deaths (no./100 person-yr)	0.16	0.20	0.10

\*Gastrointestinal symptoms included diarrhea, flatulence, nausea, and vomiting.

†P<0.0167 for the comparison with placebo.

‡Most participants with musculoskeletal symptoms had myalgia, arthritis, or arthralgia.

As far as common side effects, GI side effect and diarrhea are transient and usually pass after a week of therapy. In the DPP study, 3-5% of subjects had continuous diarrhea; this portion of subjects would be excluded in the present trial during the run-in, dose-titration period. No one had metformin associated lactic acidosis. Hypoglycemic events were either not in evidence or reported.

Weight loss is a common occurrence with metformin and will be monitored. In such a case some patients may complain of hypoglycemic symptoms (rapid heartbeat, feeling light-headed or fainting, and nausea), and in this case subjects will be asked to refrain from taking their next dose. Subjects may not need medical interventions, but will be given instruction for fruit juice or other carbohydrate and to call the coordinator immediately to come in for a blood glucose check. Levels will be checked by finger (Accucheck) and labs to LabCorp to confirm levels. If blood glucose levels are < 60 mg/dL they will be removed from the study and replaced by an additional participant. No more side effects were noted in the elderly; in fact, they had a better adherence to therapy. Young and elderly had the same rates of GI side effects and diarrhea.

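### Minor: a crossover model with end-of-phase pill-count adherence as a covariate should be labelled descriptive, because its metformin coefficient can be biased even when metformin has no effect

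*Combined protocol and SAP*

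**What the plan says.** The Medication adherence paragraph (Other Data) is motivated by the possibility that "there may be inter-individual variability in adherence to the medication". On measurement it says: "At the end of each phase, participants will be asked to return any unused pills for a pill count". ITT is primary, and "secondary analyses will include adherence as a covariate".

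The Analytical Plan gives the crossover model: "The factors in the analysis will include the baseline measure, sequence, participant within sequence, period, and metformin treatment". Adherence is not in that list. Neither section says whether adherence has one value per period or one per participant, whether it interacts with treatment, or what effect the secondary analysis should estimate. The Analytical Plan puts the weight on estimates and 95% confidence intervals.

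Two other places bear on the point. Table 3 under Risk to participants, in the row "Gastrointestinal symptoms (no. of events/100 person-yr", gives 77.8 for metformin and 30.7 for placebo in the cited prevention study. The text below it describes these effects as short-lived and expects people with continuous diarrhea to leave during titration. Interventions and Interactions allows the regimen to be modified individually for side effects.

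**The concern.** A pill count is taken after randomisation, and treatment can change it. Adjusting for it compares metformin with placebo at equal pill-taking, which randomisation does not protect. A single adherence slope also treats metformin and placebo pills alike, although only metformin pills carry drug.

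If the adjusted coefficient were reported beside ITT, a reader would probably take it as the effect of metformin allowing for adherence. In a pilot meant to supply preliminary estimates for a larger programme, a number without a clear meaning could be carried forward.

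**Working it through.** The documents give no adherence figures and no calculation to reproduce. All adherence inputs below are assumptions. Design gives 35 participants and Interventions and Interactions gives 15 + 15 = 30, so both sizes are used.

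**1. One adherence value per participant.** With 30 participants, the columns for participant, period and treatment have rank 30 + 1 + 1 = 32. Adding a participant-level adherence column leaves the rank at 32. The treatment estimate is the ITT estimate.

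**2. One value per period, main effect, no confounding.** Let D be the metformin-minus-placebo difference within a person. Set the full-dose effect to 1 and let it be proportional to metformin taken. Adherence means are mM and mP, SDs sM and sP, correlation ρ. Regressing D on the adherence difference gives

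- slope b = (sM² − ρ sM sP) / (sM² + sP² − 2ρ sM sP)
- metformin coefficient a = mM + b (mP − mM), while ITT = mM.

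The grid is sM and sP each 0.10 or 0.20, and ρ = 0, 0.3, 0.5 or 0.8 (16 combinations). The extremes, both at ρ = 0.8, are:

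- sM = 0.10, sP = 0.20: b = (0.010 − 0.016)/0.018 = −0.333
- sM = 0.20, sP = 0.10: b = (0.040 − 0.016)/0.018 = 1.333

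| Mean adherence, metformin / placebo | ITT | Adjusted coefficient |
|---|---|---|
| 0.90 / 0.90 | 0.90 | 0.90 in all 16 |
| 0.80 / 0.90 | 0.80 | 0.77 to 0.93 |
| 0.80 / 0.95 | 0.80 | 0.75 to 1.00 |

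In the second row, for example, 0.80 − 0.333 × 0.10 = 0.767 and 0.80 + 1.333 × 0.10 = 0.933.

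**3. No drug effect, shared within-period cause.** The bias in SDs of D is gap × r. Here gap is the mean adherence difference divided by the SD of the within-person adherence difference, and r is the correlation of that difference with D. To tie the gap to Table 3, assume each gastrointestinal event costs the same amount of adherence:

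- Events per three-month period: 0.778 × 0.25 = 0.1945 and 0.307 × 0.25 = 0.0768; excess 0.1178.
- Gap with Poisson counts: 0.1178/√0.2713 = 0.226. With independent yes/no events: 0.1178/0.477 = 0.247. With excess events only: 0.1178/0.322 = 0.365.
- Adherence variation unrelated to events, of k times the event variance, divides the gap by √(1 + k): 0.160 to 0.258 at k = 1, and 0.101 to 0.163 at k = 4.

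With r assumed 0.1 to 0.3, the bias is 0.02 to 0.11 SD (k = 0), 0.02 to 0.08 (k = 1) or 0.01 to 0.05 (k = 4). Simulation (30,000 trials per setting) agrees. At gap 0.37 and r = 0.1, 0.2, 0.3, type I error is 5.2, 6.4, 8.5% (n = 30) and 5.5, 6.9, 9.3% (n = 35). At r = 0 it is about 5%.

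For scale, the ITT 95% half-width is 2.048/√30 = 0.374 SD or 2.035/√35 = 0.344 SD. The largest bias, 0.111, is 30% or 32% of that. This range is not a bound. With assumed means 0.80/0.90, SDs 0.15/0.10 and ρ = 0.5, the gap is 0.10/√0.0175 = 0.76, and r = 0.3 would give 0.76 × 0.3 = 0.23 SD.

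**4. Adding adherence by treatment.** This removes the shared slope but not the confounding. In confounded simulations at n = 30, the estimate at full adherence was 0.59 to 1.42 for a true 1.0, and 0.22 to 0.41 for a true 0.

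**5. Instrumental variables.** The estimate is ITT divided by mean metformin adherence. With no drug effect it stayed at 0.00 even with confounded adherence. With a proportional dose response it returns 1.00 by construction. Two assumptions matter:

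- *Dose response.* With mean metformin adherence 0.80, the curve 1.3A/(A + 0.3) gives 0.945 at A = 0.80, and 0.945/0.80 = 1.18. Across this curve, 1.5A/(A + 0.5) and a plateau at 75% of doses, the estimate is 1.15 to 1.22 for a true 1.00. The covariate coefficient is 0.93 to 1.02.
- *Carryover.* If a fraction c of the effect persists to the end of the placebo period in the metformin-first sequence, ITT and the instrumental-variable estimate are both multiplied by 1 − c/2. For c = 0.10, 0.25, 0.50 the latter is 0.95, 0.875, 0.75. The schedule has "Dispense New Medication" at the Mid visit and shows no washout. The statement that metformin "has an average elimination half-life of 6.2 hours in plasma" concerns the drug, not how long an expression or methylation change lasts. The only planned check is "We will explore for the metformin by sequence interaction".

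**The case against.** The strongest reply is that the plan is judged against a target it never sets. A reader might infer from the contrast with ITT that the analysis claims to estimate metformin as taken. The text does not say so, and its wording about variation between individuals fits participant-level coding, which is harmless, just as well. That stands, and the point is therefore conditional on per-period coding.

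The sizes also rest on assumed adherence. In the 0.80/0.90 grid, 14 of 16 coefficients lie above ITT, towards the full-dose effect, one equals it and one falls below. The one below needs adherence to be more variable on placebo, contrary to the gastrointestinal mechanism. Confounding is plausible from Table 3 but not shown, and the same section says the symptoms pass. A reader might conclude that the trial's adjusted estimate will be biased; the documents do not support that.

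Nor do they support the inference that instrumental variables are always better. Under the saturating curves above, the covariate coefficient is nearer the full-dose effect. The alternative also only rescales ITT, so differences in adherence between people, the plan's stated reason, drop out of it.

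What remains is the null: under randomisation the instrumental-variable estimate stays at zero when metformin does nothing, and the covariate coefficient need not.

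**Conclusion.** The point holds as a minor one. With per-period main-effect coding, the metformin coefficient departs from ITT whenever mean adherence differs between treatments, by an amount the plan cannot predict. With a shared within-period cause as well, it is biased under no drug effect: about 0.01 to 0.11 SD and type I error about 5 to 9%, given gaps derived from Table 3 and r of 0.1 to 0.3. A wider adherence gap would give more; equal mean adherence or zero correlation would give none. With participant-level coding the analysis adds nothing to ITT. The primary ITT analysis does not use adherence and is untouched.

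**What to change.** Keep ITT primary and replace the adherence sentence with text such as:

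> Models that include adherence as a covariate are descriptive, and their treatment coefficient will not be reported as an estimate of the metformin effect. If an adherence-adjusted effect is reported, it will be a sensitivity estimate by instrumental variables in the same crossover model, with randomised treatment in each period as the instrument for the fraction of metformin taken by pill count (zero in the placebo period). The fraction is of the [planned / modified] schedule. The assumptions will be reported with it: assignment acts only through metformin taken, pill counts are accurate, there is no carryover, and the dose response is linear.

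The denominator matters because regimens can be modified. Suppose, as an illustration, 20% have their schedule halved and everyone takes 90% of their own schedule. The planned fraction is then 0.90 × (0.80 + 0.20 × 0.50) = 0.81. With a proportional full-dose effect of 1, ITT is 0.81, and the estimate is 0.81/0.81 = 1.00 on the planned schedule or 0.81/0.90 = 0.90 on the modified one.

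The cost is a few sentences and at most one extra model on pill counts already collected. The downside is that the estimate adds no power, overstates the full-dose effect if the response saturates, and shrinks with carryover as ITT does. It should not be presented as correct in every case.
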